Minimal observable impairments in speech. The patient may present subjective difficulties that are not evident to the listener.	5

e) **Evaluation of satisfaction when performing rehabilitation therapy.** The characterization of the patient's perception of satisfaction will be evaluated by the same neuropsychologist, who will be blinded to the treatment the patient is receiving, using the Intrinsic Motivation Inventory (IMI). The IMI is a multidimensional measurement device intended to assess the subjective experience of participants related to an objective activity in experiments; it has been used in various experiments related to intrinsic motivation and self-regulation. The instrument assesses participants' interest/enjoyment, perceived competence, effort, value/utility, felt pressure and strain, and perceived choice while performing a given activity, yielding six subscale scores. The concepts of perceived choice and perceived competence are theorized to be positive predictors of both self-report and behavioral measures of intrinsic motivation, and pressure/strain is theorized to be a negative predictor of intrinsic motivation. Effort is a separate variable that is relevant to some motivation questions, so it is used as relevant. The value/utility subscale is used in internalization studies, with the idea that people internalize and self-regulate with regard to activities that they experience as useful or valuable to themselves.

The subscales and items are:

Intrinsic Motivation Inventory (Assessment of satisfaction when performing rehabilitation therapy)
 (Spanish versión)

	Reality Virtual			Restriction and Induction of Movement			TF and TO habitual		
Patient perception	Ini. Val.	Interm. Val.	Fin. Val.	Ini. Val.	Interm. Val.	Fin. Val.	Ini. Val.	Interm. Val.	Fin. Val.
Interest and satisfaction with treatment									
As he worked on the task he thought how much he enjoyed it.									
I found the task very interesting.									
Doing homework was fun.									
I really enjoyed doing homework.									
I thought the homework was very boring (R).									
I seemed the task very interesting.									
I would describe the task as very pleasant.									
Perception of competence (of the patient versus the treatment)									
I think I'm very good at this task.									
I think I did very well in this activity, compared with other									
I am satisfied with my performance in this task.									
I felt quite skilled at this task.									
After working on this task for a while, I felt quite competent.									
Effort and importance of treatment									
I felt it was my choice to do the task.									
I didn't really have the option to do task (R).									
I felt like I was doing what I wanted to do while working on the assignment.									
I felt that I had obligation to do task (R)									
I did the homework because I had no other option (R).									
Stress or strain (caused by treatment)									
I didn't feel nervous about doing task (R).									
I felt tense while doing task.									
I felt relaxed while doing task (R).									
I was anxious while doing task.									
I felt stressed while doing task.									

Ini. Val.: initial valoration; Intermed. Val.: intermediate valoration; Fin. Val.: final valoration.

Subscale scores can be used as dependent variables, predictors, or mediators, depending on the research questions being addressed. The higher the score, the higher the satisfaction.

3. Therapy programs.

- a. Virtual reality program. The activities indicated in the tennis and ski software for the upper limb, covering cracks for both limbs and Star Wars-battles in the galaxy for the hand and fine pincer,

which will be carried out with the interface of the virtual reality equipment "connected" to the patient through movement sensors, with the multiperceptual feedback of the Kinect equipment or with googles.

b. *Movement restriction and induction therapy.* The patient will be placed a sling on the "healthy" thoracic limb, attached to the thorax, through a bra, gently but firmly, in such a way that it does not alter circulation or compress peripheral nerves. It will be explained to you that you should do all your activities with the "sick" member, to the extent possible. The restriction of the healthy side forces the patient to put all his effort into carrying out the activities of daily life, simulated during the therapy. This restriction will be carried out for 1 hour in therapy in the medical unit. And the patient will be told to repeat it at home at least once a day for one to five hours, without receiving support from family members while wearing the sling.

c. *Regular physical and occupational therapy.* The specific activities are shown in Annex 1. They include:

- **Motor management:** tasks to promote mobility of the shoulder, elbow, pentadigital clamp, fine clamp, transfers; volitional movements, eye-motor coordination, hip, knee, ankle and gait mobility.
- **Sensory training:** deep sensitivity, stereognosis, sensory discrimination, graphesthesia, topognosis and proprioception.

4. *Concentration and analysis of information.* The results of the different evaluations will be noted on the information capture sheet (Annex 2 and 4); Subsequently, they will be entered into an Excel spreadsheet and finally exported for analysis to the SPSS V-19 program.

STATISTICAL ASPECTS

Sampling

Non-probabilistic, of consecutive cases.

Sample size

The sample size calculation was performed to test the working hypothesis* (average difference of 38.6 points and a SD 12.23), with a standardized effect size greater than 1 in a prefabricated table to establish mean differences (Appendix 1. 13 -A)⁵², considering a unilateral hypothesis, in a finite population and without replacement, with a value $\alpha = 0.05$ and $\beta = 0.10$.

For 17 patients plus 20% of possible losses, for a total of 19 patients per group.

* The score of the motor evolution evaluated with the Fugl-Meyer scale was considered, with therapy supported by virtual reality, found in the study of the unit, considered as a pilot^{47, 48}.

Statistic analysis

Descriptive statistics will be carried out for the qualitative variables through tables, graphs and percentages; for the quantitative ones, measures of central tendency and its corresponding dispersion will be used, depending on the distribution of the data. The distribution of the numerical data will be compared with the distribution curve using the Shapiro-Wilk test, depending on the result, the ANOVA or Friedman test will be used for intragroup comparison; for comparison between groups, ANOVA of repeated measures or the Kruskal-Wallis test will be used. In case of detecting variables that could be potentially related to the result, correlation tests such as Pearson or Spearman will be applied. An α value of 0.05 will be considered.

ETHICAL ASPECTS

This research respects the institutional, national and international standards that govern research on human beings in our country. Including the General Health Law, TITLE FIVE Research for Health, sole chapter ⁵³; the regulation of the General Law of Health in Matters of Research for Health ⁵⁴; and the Official Mexican Standard NOM-012-SSA3-2012, which establishes the criteria for the execution of research projects for health in human beings ⁵⁵.

Considering what is specified in the regulation of the General Health Law, second title of the Ethical Aspects of Research in Human Beings chapter I, the present work was considered as research with greater than minimum risk, since the techniques to be contrasted, although they are considered as moderate therapeutic exercise, they are based on activities included in classic physical and occupational therapy -common in patients with a cerebrovascular event in the rehabilitation unit-, but they will be supported and carried out with unusual or computerized devices and changes are expected to occur in brain architecture, evident by clinical changes, since imaging studies will not be performed.

Article 17. III. Research with greater than minimal risk: are those in which the probabilities of affecting the subject are significant, among which are considered: radiological and microwave studies, drug trials and modalities defined in article 65 of this Regulation, trials with new devices, studies that include surgical procedures, blood extraction of 2% of the circulating volume in neonates, amniocentesis and other invasive techniques or major procedures, those that use random methods of assignment to therapeutic schemes and those that are controlled with placebos, among others .

The signature of the informed consent letter will be requested, by the patient or relatives. A detailed explanation of participation will be provided and anonymity will be ensured at all times. Likewise, it will be guaranteed that in case of not accepting or suspending the participation, this will not affect the management received by the institute. In this case, the patient will go to the regular consultation of the doctor in office 16.

This research project was submitted for consideration by the local research and research ethics committee, where it was verified that it met the necessary requirements to be carried out and was authorized with the registration number **R -2016-3702-44**.

RESOURCES

Human Resources

1. A PhD student and person in charge of the project
2. A consultant with a doctorate in Medical Sciences and a specialist in rehabilitation medicine
3. Two advisors with doctorates in medical sciences and specialists in Internal Medicine
4. A physician specializing in rehabilitation medicine for blinded assessment of patients
5. A doctor specializing in rehabilitation medicine for regular consultation and monitoring of patients
6. A psychologist with a master's degree in neuropsychology for mental evaluation
7. A physical therapist
8. An occupational therapist

Material resources

1. Physical and occupational therapy materials: buckets, jars, wood, etc.
2. A virtual reality equipment and accessories (googles, sensors).
3. A 50 or 60-inch screen compatible with the Xbox One Kinect.
4. Office supplies

Economic resources

The infrastructure of the rehabilitation unit will be used, which has spaces for the management of patients with cerebral vascular event, as well as most of the necessary supplies for the production of stationery and physical and occupational therapy materials.

FINANCING

Funding was not obtained to purchase virtual reality equipment and supplementary materials for physical and occupational therapy, so we worked with 2 equipment owned by the participants. The occupational therapy materials were those of the Medical Unit where the patient was treated. The participating personnel are experts in the area and contributed to the acquisition of materials and equipment, mainly the doctoral student.

FEASIBILITY

Approximately 32 patients per month with a diagnosis of cerebrovascular event and with the necessary characteristics to enter this study attend the rehabilitation unit. There is broad support from the authorities to carry out the research and permissions would be granted to the participants to carry out the activities in a timely manner. Therefore, it is considered that the study is feasible to be completed within the scheduled time.

DIFFUSION

At the conclusion of this work, the results will be disseminated in the different research forums of the IMSS, as well as within the rehabilitation units for their knowledge. It is also intended to be published in a journal with impact, as well as to take it to national or international congresses of the specialty.

TRANSCENDENCE

With the proposed methodology, it is expected that the results are considered generalizable to the population. It is intended that they be seriously considered as a therapeutic tool in the different rehabilitation units or medical units that have physical or occupational therapy personnel (first and second level), which could impact the care of these patients. It can even affect the cost of the same patient who would not have to go to a medical unit for check-ups or reinforcements, due to the fact that virtual reality equipment can currently be found in private homes, on the one hand; on the other, adherence to the treatment described (if verified) would allow a continuous evolution towards improvement with the need for sporadic medical review.

BIOSECURITY ASPECTS

Does not apply.

SCHEDULE OF ACTIVITIES

Gantt chart

Start month: Mz = March 2017 (an important delay in the scheduled activities is accepted, related to the earthquake of 2017 and the pandemic in 2020)

	2018-19*	2020-21* *	2022	2023	2024	2025														
Month	T*	En-Dc	En-Dc	En-Dc	En	...	Dc	En	...	Dc	...	En	...	Dc	En	...	Dc	En	...	Dc
Modifications of research in doctoral seminars	P* X X X																			
	R* X X X																			
Standardization of procedures	P* X X																			
	R* X X																			
Recruitment, evaluation and patient monitoring	P* X X X X X																			
	R* X X X X X																			
Analysis and writing of Results partial/final	P* X X X X X																			
	R* X X X X X																			
Preparation of final report partial/final	P* X X X X X																			
	R* X X X X X																			
manuscript writing for publication	P* X X X X X																			
	R* X X X X X																			
Send to publication	P* X X X X X																			
	R* X X X X X																			

* México city, earthquake of 2017: structural damage and partial suspension of the therapy service of the physical medicine and rehabilitation unit

** COVID19 pandemic: suspension of the therapy service for patients with stroke sequelae in the physical medicine and rehabilitation unit.

T* = Tiempo P* = Programado R* = Realizado

REFERENCES

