Because the central nervous system has a somatotopic distribution, ischemia in the MCA territory will affect the contralateral side for motor activity and the ipsilateral side for sensory activity. After a CVE, the presentation of neurological impairment depends on the location and size of the lesion. The territory most frequently affected is that of the left middle cerebral artery (LMCA) and the most common motor deficit is hemiplegia or hemiparesis, with or without aphasia, affecting the extremities and muscles of the lower contralateral hemiface². The loss of voluntary movement can be accompanied by alterations in sensation throughout the length of one of the sides of the body, although there can be variations in the clinical presentation related to perilesional disorders²⁰. When the acute phase is over, almost always the limb² The lower one has a greater tendency to recover than the upper one. At 3 months, a large percentage of hemiplegics already begins to walk, while the upper limb is more difficult to recover and, of these, approximately 40-45% experience major hand problems. In the condition of the upper extremity, 44% of patients recover motor activity and 40% present minimal or no recovery. The sensory pathways play an important role in motor control, since severe sensory alterations produce disability similar to paresis and a poor recovery of motor function, worsening the functional prognosis²¹.

After a stroke, people who survive have a high risk of developing a wide range of secondary conditions such as pain, depression, pressure ulcers and falls, among others, during the acute or post-acute recovery period; there may also be balance disorders and functional dependence, which is why basic daily life activities oriented towards caring for one's own body are compromised, such as dressing, eating, etc., which causes incapacity for work and limitations in quality of life¹⁶.

NEURO-REHABILITATION

Rehabilitation techniques aimed at improving hemiparesis vary their objectives, depending on the evaluations and the therapeutic approach, since a way is sought to explore the patient's capacities that can improve their autonomy. Neuromuscular rehabilitation is based on teaching-learning techniques such as performing and reproducing movements²².

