Score	Action/ Movement	Initial valoration	Intermedia valoration	Final valoration
Sitting patient 0: no movement 9: palpable contraction 14: perform movement but not full range vs gravity 19: full range of motion vs gravity but not vs resistance 25: movement vs resistance but less than contralateral 33: normal strength	1. Shoulder abduction 2. Elbow flexion Voluntary movement of 90°			
0: no movement 11: prehension starts 19: takes the cube but is not able to hold it vs gravity 22: he takes the cube and is able to hold it vs gravity but not vs resistance 26: take the cube overcomes gravity and resistance but is less than the contralateral 33: regular clamp	3. Grasp Hand: 2.5 cm cube between thumb and other fingers.			
0: no movement 9: palpable contraction 14: perform movement but not full range vs gravity 19: full range of motion vs gravity but not vs resistance 25: movement vs resistance but less than contralateral 33: normal strength	4. Hip flexion 5. Knee extension 6. Ankle dorsiflexion			
Upper limb Index: $1+2+3+(1)/100$				
Lower limb index: $4+5+6+(1)/100$				
Total motor index: (Motor Index of UL + Motor Index of LL/2)/100				

Indicators. The application process is described in the procedures section. They will always be performed by the same doctor, who will ignore which therapy group the patient corresponds to, at the beginning, at 6 and 12 treatment sessions.

The equivalence of the results for the Motor Index is considered based on 100 total points (sum of upper limb + lower limb divided by 2).

Qualification	Equivalence
- 100 a 90 points.	Independent patients with rehabilitation for work adjustment and activities of daily living.
- 89 a 80 points.	Independent patients with limitations, who need integral rehabilitation treatment.
- 79 a 70 points.	Semi-dependent patient who needs external help and orthotics.
- 69 a 60 points.	Patients with help-dependent limitation.
- Less 60 points.	Dependent patient needs prolonged rehabilitation.

The equivalence of the results for the Fugl-Meyer scale is considered based on 100 total points, taking into account only the motor aspect of the lower and upper limb (maximum of 66 points for the upper limb + 34 points for the lower limb). The original equivalence established by the author in 1980 and the most recent one proposed by other authors are shown.

Fugl-Meyer (1980)	Duncan, Goldstein, Horner, Landsman, Samsa y Matchar (1994)
<50 = Severo	0-35 = Muy severo
50-84 = Marcado	36-55 = Severo

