Patients with a diagnosis of cerebrovascular event (CVE) will be recruited upon arrival at the PMRUcXXI in the first-time appointment area. The diagnosis will be verified and an appointment will be made to the office of one of the researchers (evaluator 1). During the appointment the purpose of the study will be explained and doubts will be clarified. Whether they accept or not, the patient will receive the consultation that is normally provided to this type of patient and the information will be recorded in the clinical record. If patient do not accept, after the consultation, the appropriate management for your condition will be prescribed and a subsequent appointment will be made with the corresponding doctor to continue the control. In case of agreeing to participate, a summary will be made in Annex 4, which includes demographic data, whether or not is a worker, the need for temporary disability for work and clinical data for the research file. The signature of the informed consent letter will be also requested (Annex 3). This physician 1 will assign the therapeutic modality by using a table of random numbers to: Group 1. Therapy supported by virtual reality; Group 2. Therapy supported by constraint-induced movement; o Group 3. Usual physical and occupational therapy. An appointment will then be made to be assessed by the second doctor (evaluator 2), who will remain blind to the treatment, and will measure the functionality of the thoracic and pelvic limbs with the different scales, described in the procedures section, including muscle tone, trophism, ranges of mobility, functionality of the limbs, as well as of the hand, coordination, balance, sensory aspects and language (Annex 2). The limb functionality scales will be applied before (initial assessment -V.I.), during (intermediate assessment -V.Int.- week 3, session 6) and after (final assessment -V.F.- week 6, session 12) of the performance of the different rehabilitation programs. At the same times, the Boston Aphasia Intensity Scale and the Intrinsic Motivational Inventory will be applied by a neuropsychologist blinded to the treatment.

Procedures.

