2. Extremity motor assessment. The patient will be admitted to consulting room 22, by appointment, where he will be received by physician 2 (blinded evaluator), who will have the indication to address the patient specifically in relation to obtaining data during the physical examination (actions to obtain the evaluation with scales). He will introduce himself and establish a rapport with the subject, but remind him that this assessment is related to an investigation and insist that he not give more information than what he requests. The evaluating physician will not know the therapeutic modality that the patient will receive. Afterwards, he will ask you to sit on the examination table and the clinical review related to the functionality of the hemibody will begin. The evaluation will begin with the motor index scale, then the quality of the fine forceps will be measured, and finally the Fugl Meyer scale. The assessment will be made before starting therapy, half the number of sessions (3 weeks) and at the end of treatment (6 weeks).

- a) **Evaluation with Fugl Meyer scale.** This scale is specific to the Cerebral Vascular Event, designed with the objective of measuring the motor deficit, balance, sensitivity and state/pain of the joints of patients who present hemiplegia/hemiparesis as a consequence of the event. In clinical practice it helps to assess the severity of the deficit, describe motor recovery, plan rehabilitation treatment and monitor the clinical evolution of patients after a stroke.

The result of this scale is measured in a numerical score, the higher numerical score corresponds to a better state of the patient's functioning. The scale is built to give ratings separately (both members, balance and sensitivity), but it can also be used globally, with a maximum of 226 points. The questionnaire must be administered by the evaluating physician, it contains 113 items encompassed in 5 domains that in turn cover three dimensions of the state of functioning and functionality in the EVC. For each item, the examiner must grant the corresponding qualifications indicated in each section.

Fugl-Meyer scale (spanish versión).

Dimension: Assessment of motor function in the upper limb.

Dominio	Item	Ini. Val.	Interm. Val	Fin. Val.
I. Osteotendinous reflexes 0: no reflexes 2: reflexes are obtained	1. Biceps 2. Triceps			

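### Baseline sensation is named as prognostic and scored before therapy, but the between-arm motor comparison adjusts for no baseline covariate, so some precision may be lost

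*Combined protocol and SAP*

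**What the plan says.** **Prognosis.** The Background, under Clinical manifestations, states that "severe sensory alterations produce disability similar to paresis and a poor recovery of motor function, worsening the functional prognosis".

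**Measurement.** The Fugl-Meyer table (Variables, Motor function of the thoracic limb and pelvic limb) has a sensitivity domain of 12 items: 4 exteroceptive (0 to 8) and 8 proprioceptive (0 to 16), 0 to 24 in all. Study General description and Procedures, item 2, have the blinded evaluator apply the scale before therapy, at session 6 and at session 12.

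**Outcome.** The Indicators text in the same Variables section interprets the Fugl-Meyer result out of 100 points, "taking into account only the motor aspect of the lower and upper limb". Sensation is then outside the score. Procedures, item 2a, also allows the global 226-point total, which contains it.

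**Allocation.** The treating physician is to "assign the therapeutic modality by using a table of random numbers". No stratification is described.

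**Analysis.** Under Statistic analysis, "for comparison between groups, ANOVA of repeated measures or the Kruskal-Wallis test will be used". No covariate is named. The only clause on other variables reads: "In case of detecting variables that could be potentially related to the result, correlation tests such as Pearson or Spearman will be applied".

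**The concern.** The protocol names a prognostic factor and collects it before treatment, but uses it neither in the allocation nor in the arm comparison. The correlation clause does not fill the gap. It is triggered by what is found in the data, and a Pearson or Spearman coefficient leaves the difference between arms unadjusted.

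What is at stake is efficiency. Any outcome variance that baseline sensation explains, over and above the baseline motor score, stays in the error term. With 17 to 19 patients per arm, a modest reduction in that term is worth having, and here it needs no extra data. The protocol also faults earlier trials for ignoring patient factors such as severity of the condition (Background, on the reviews of virtual reality) and says in the Justification that it means to remedy their deficiencies.

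**Working it through.** **Inputs from the documents** (Sample size, and Table 13.A in Appendix 1): one-sided α = 0.05, β = 0.10, 17 per group before losses, SD 12.23. The table row that yields 17 is a standardised effect of 1.00.

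**Input not in the documents:** R², the share of residual variance in the 6-week motor score that baseline sensation explains. It is assumed, over 1% to 20%. The 1-SD effect is measured on the residual SD before sensation is added.

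**Step 1, the plan's own figure.** n per group = 2(1.645 + 1.282)² / 1² = 17.1, in line with the table's 17.

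**Step 2, power without the covariate.** Noncentrality = √(17/2) = 2.915, with 17 + 17 − 2 = 32 degrees of freedom. One-sided power from the noncentral t is 88.6%, slightly under the planned 90% because the table figure is close to the normal approximation.

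**Step 3, power with the covariate.** Noncentrality = √(17/2) / √(1 − R²), with 31 degrees of freedom. The standard error is multiplied by √(1 − R²). At SD 12.23 the unadjusted SE is 12.23 × √(2/17) = 4.19 points.

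| Assumed R² | SE factor | SE (points) | One-sided power |
|---|---|---|---|
| 0 (no covariate) | 1.000 | 4.19 | 88.6% |
| 1% | 0.995 | 4.17 | 88.9% |
| 5% | 0.975 | 4.09 | 90.0% |
| 10% | 0.949 | 3.98 | 91.3% |
| 20% | 0.894 | 3.75 | 93.9% |

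Spending a second degree of freedom on the baseline motor score changes these power figures by less than 0.1 percentage point.

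**Step 4, validity of the unadjusted test.** Chance imbalance between randomised arms is already part of the standard error. In a simulation with no treatment effect, 17 per arm and sensation correlated 0.3 or 0.5 with the outcome, the unadjusted one-sided test rejected in 5.0% and 5.1% of trials. Type I error is therefore not at issue.

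**The case against.** **Two stronger inferences that the documents do not support.**

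*That a chance imbalance in sensation could by itself produce the pilot's virtual reality advantage.* Table 1 gives changes of 12.77 and 10.9, a difference of 1.87 points. With SD 12.23, a correlation of 0.3 to 0.4 and an imbalance of 0.5 SD, the shift is 0.3 × 0.5 × 12.23 = 1.83 to 0.4 × 0.5 × 12.23 = 2.45 points, which seems to match. But 12.23 is the control group's SD at baseline, while 1.87 is a difference in change. Using the pilot SDs and assumed pre-post correlations of 0.5, 0.7, 0.8 and 0.9, the change SD is about 11.4, 8.9, 7.4 and 5.4. The same imbalance then shifts the estimate by 1.71, 1.34, 1.11 and 0.81 points at correlation 0.3, and by 2.28, 1.79, 1.48 and 1.09 at 0.4. Only one of the eight reaches 1.87. In any case 1.87 is small beside a standard error of 4.19, so most chance variation could match it.

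*That sensation acts differently by arm.* The usual program lists training in "deep sensitivity, stereognosis, sensory discrimination, graphesthesia, topognosis and proprioception", and the virtual reality program in Procedures, item 3, lists no such component. That is an inference from the content of the programs, not evidence of an interaction. The protocol also describes virtual reality as giving tactile sensory input, and a main-effect covariate would neither test nor remove an interaction.

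**Objections that stand in part.**

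- A repeated-measures ANOVA that includes the initial value already reflects change through its group-by-time term. Sensation helps only through what it adds beyond baseline motor level, and no such coefficient is given.
- The Background sentence concerns severe sensory loss. Entry requires Brunnstrom of at least 4 and Ashworth of at most 2, and the spread of sensory scores in such patients is unknown. A narrow spread would leave little to gain.
- Sensation alone would be an odd choice of covariate. The baseline motor score is the more obvious one, and Kruskal-Wallis can take neither.

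These limit the expected gain and shape the remedy. They do not supply the missing adjustment.

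**Conclusion.** The point holds as a matter of precision. The plan names sensation as prognostic, measures it before treatment and leaves it out of the arm comparison. The planned unadjusted test is still valid.

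The gain is modest and uncertain: from 88.6% power to between 90.0% and 93.9% if sensation explains 5% to 20% of residual variance, and negligible at about 1%. These figures rest on the plan's one-sided 0.05 test, 17 analysed per group, a 1-SD effect, a linear relation and an R² that is assumed throughout. Adjustment would not make the trial informative about an effect as small as the pilot's. At SD 12.23, one-sided power for 1.87 points is about 11.5% unadjusted and 11.9% if sensation correlates 0.3 with the outcome (normal approximation).

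**What to change.** In Statistic analysis:

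1. Prespecify a linear model (or a mixed model using the session-6 and session-12 visits) for the 6-week Fugl-Meyer motor score, with arm, baseline motor score and baseline sensitivity score (0 to 24).
2. Report the adjusted virtual-reality-versus-usual and restriction-versus-usual differences, each with a 95% CI.
3. If model assumptions fail, use a rank-based ANCOVA with the same covariates in place of Kruskal-Wallis.
4. State that the outcome is the 100-point motor score, not the 226-point total. Sensation would otherwise be both covariate and part of the outcome. The hypothesis names the upper limb only; if its 66-point subscore is meant, say so. The covariate argument is unchanged.

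**Cost.** Wording in the plan and one or two degrees of freedom. Both scores are already due from the blinded evaluator at the initial visit. The downside is little return if sensory scores vary little among eligible patients. Fixing the covariates in advance also removes the temptation to choose them after seeing the correlations.
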